22-008247

Validation and feasibility of patient self-sampling of HPV for cervical cancer screening

NCT05600283

Document Date: 11/17/2023

IRB Minimal Risk Protocol Template

Note: If this study establishes a human specimen repository (biobank) for research purposes, do not use this template. Use the Mayo Clinic Human Specimen Repository Protocol Template found on the IRB home page under Forms and Procedures at <http://intranet.mayo.edu/charlie/irb/>

First-time Use: Use this template to describe your study for a new IRB submission.

1. Complete the questions that apply to your study.
2. Save an electronic copy of this protocol for future revisions.
3. When completing your IRBe application, you will be asked to upload this document to the protocol section.

Modification: To modify this document after your study has been approved:

1. Open your study in IRBe. Click on the study 'Documents' tab and select the most recent version of the protocol. Save it to your files.
2. Open the saved document and activate "Track Changes".
3. Revise the protocol template to reflect the modification points, save the template to your files
4. Create an IRBe Modification for the study and upload the revised protocol template.

General Study Information

Principal Investigator: [name]

Study Title: Validation and feasibility of patient self-sampling of HPV for cervical cancer screening

Protocol version number and date: Version 5 on 11/17/2023

Research Question and Aims

Hypothesis: Patient self-sampling for vaginal HPV infection using the Evalyn collection swab device will generate comparable results (defined as sensitivity of $\geq 90\%$; specificity of $\geq 95\%$) to the gold standard of a clinician-collected cervical sample for HPV testing.

Aims, purpose, or objectives: Primary aim is to validate a patient self-sampling vaginal collection kit and laboratory testing for the detection of HPV infection. Secondary aim is to assess the patient perspective on acceptability and feasibility of a self-sampling approach to cervical cancer screening through a survey of study enrollees.

Phase 2 aims: Validate a patient self-sampling vaginal collection kit that is mailed to the patient, collected at home, mailed back to Mayo Clinic for HPV testing and compared with HPV test results from a clinician-collected cervical sample. Assess the patient perspective on acceptability and feasibility of a self-sampling approach to cervical cancer screening at home through a survey of study enrollees.

Note: Phase 1 (original IRB submission) involved study subject self-collection conducted on the Mayo Clinic campus and compared with a clinician-collected specimen with transport of both specimens within Mayo campus to the Mayo lab.

Phase 3 Aim - Stability testing: Mayo Virology Lab will conduct time-based pre-processing stability testing and temperature extremes stability testing of Evalyn brush samples to ensure that time-delay in receipt and processing of Evalyn brush samples and exposure to hot and cold temperatures will not impact the HPV test results.

Background (*Include relevant experience, gaps in current knowledge, preliminary data, etc.:*)

Cervical cancer is preventable through screening and treatment of pre-cancers yet estimates from the American Cancer Society (ACS) predict 14,100 cervical cancer cases and 4,280 deaths in the US in 2022, which occur most often in never or under-screened women. (1) Data from National Health Information Survey (NHIS) illustrate a concerning trend with a decline in screening rates from 2000 (86.5%) to 2018 (81.1%). (2, 3) Cervical cancer screening rates may be even lower as NHIS results are based on self-reported data which have been shown to over-estimate actual rates. (4) Only 64.6% of screening-eligible women in Olmsted County were up to date with cervical cancer screening using data from confirmed diagnosis and billing codes (5) falling well below the Healthy People 2030 goal of 84.3%. (6) Disparities in screening are associated with sociodemographic factors including race and ethnicity, household income, education, sexual orientation and geography. (6) As well, marked declines in cervical cancer screening were noted early in the COVID-19 pandemic. Compared with one year prior, screening rates among women aged 30-65 years in Kaiser Permanente of Southern California dropped 82% during the first 3 months of the pandemic and remained 24% lower in the 3 months after lifting of a stay-at-home order. (7)

Lack of health insurance or a primary care provider are often the most significant roadblocks to cervical cancer screening completion (8) though these factors are less likely to be barriers for screening eligible women receiving primary care in Mayo Clinic Rochester. Instead, previously identified barriers that may be applicable to our population include time challenges related to work or childcare schedules (9) and inconvenient appointment times (10), discomfort with past gynecologic exams (9) or having multiple medical co-morbidities. (11) As recommended by the Community Preventive Services Task Force, effective interventions to increase uptake of cervical cancer screening incorporate multiple components addressing broader categories of increasing community demand, community access and clinician delivery of cervical cancer screening along with addressing structural barriers. (12)

With recognition that persistent high-risk human papillomavirus (HPV) infection causes cervical cancer and with development and FDA-approval of clinician-collected HPV screening tests, a paradigm shift in cervical cancer screening method from cytology-based (Pap) testing to an emphasis on HPV-based testing has occurred (13) as illustrated by the U.S. Preventive Services Task Force endorsement of primary HPV screening in 2018 (14) and ACS's preferential recommendation for primary HPV screening in 2020. (15) This evolution in screening strategy has led to a unique application of HPV screening that addresses community access and barriers to screening by involving patients in self-collection of a vaginal specimen at home (or other settings) for HPV testing. High levels of concordance have been observed between patient-collected vaginal and clinician-collected cervical samples for HPV results in multiple studies. (16) (17) In a meta-analyses of 56 test accuracy studies and 25 randomized trials, vaginal specimens collected by patient self-sampling were as sensitive as clinician-collected samples when specimens were processed on a PCR-based test platform for detecting CIN2+ or CIN3+ (pooled ratio 0.99, 95% confidence interval 0.97 to 1.02). (18) Offering at home self-sampling has been shown to increase screening uptake in under-screened women in Canada and Europe. (19, 20)

Acceptance of HPV test self-collection among diverse groups of women in low-resource settings has been observed in pilot studies performed in Appalachian Kentucky (21), with Somali immigrants in Minnesota (22), Latina and Haitian women in Miami (23), and Black women in the Mississippi Delta (24) with different test collection settings including homes, clinics and a church. Less is known about patient acceptance of self-sampling among women in higher resource settings such as the Mayo Clinic Rochester, though most women agreed that self-sampling would be more convenient, easier and less painful than clinician-collected screening in a survey conducted across Minnesota. (25) As part of this study, we will conduct a survey of accrued subjects after they have collected the self-sampled specimen to assess acceptability and feasibility of this screening method. The survey questions are based on a theoretical framework of acceptability (TFA) questionnaire designed to be adapted and applied to assess any healthcare intervention. (26)

For this study, patients will use the Evalyn brush (Rovers Medical Devices, [name], The Netherlands) for self-collection, a device that is well-studied and currently offered as an in-home vaginal self-sampling screening option through the national cervical cancer screening program of the Netherlands. (27) Design of the device resolves practical sampling issues by incorporating insertion indicator wings and “click sounds” so patients’ insert to the appropriate depth and perform adequate brush rotation. The Evalyn brush device is manufactured, packaged, and marketed by Rovers Medical Devices B.V. in Oss, the Netherlands. The Evalyn brush device is an FDA-cleared device with 510(k) status and will be used according to its cleared indication. Testing for HPV will be performed in the clinical virology lab at Mayo Clinic (Rochester, MN) on the Roche Cobas 4800 platform for phase 1 and 6800/8800 platform for phase 2, using a polymerase chain reaction-assay (PCR) that is FDA-approved for clinician-collected HPV testing, however not approved for self-collected HPV testing. In multiple studies evaluating the performance of the Evalyn brush on the Roche Cobas HPV PCR assay, strong concordance was noted between self- vs clinician-collected results (28) (29) and the self-sampled specimen test sensitivity was high/non-inferior when compared to the gold standard of a clinician-collected cervical specimens. (30, 31)

Process flow for subject self-collected and clinician-collected specimens: Subject will check in at the Gynecology desk and be roomed per usual practice. Study coordinator will meet with subject next and provide a bag containing a study card from Biospecimen Accessioning and Processing (BAP) and a labeled self-sampling Evalyn brush kit, along with printed instructions on how to use the Evalyn brush to collect the vaginal sample. The device will be labeled with patient identifiers. Subject will be directed to a private room to collect the vaginal specimen. Subject will be in or return to exam room and give specimen container to study coordinator. Study coordinator will leave the labeled clinician-collection kit (endocervical brush, spatula and ThinPrep specimen container in the exam room. The clinician providing the care for that appointment will then enter the room and will conduct a speculum exam, collecting a cervical specimen using the clinician-collection kit material describe above before performing the remainder of the visit. The clinician collection will be completed before the colposcopy or other reason for the visit.

Patient survey: After the subject has finished the self-collection and returned to the exam room, the study coordinator will give the subject an iPad to complete the REDCap electronic acceptability and feasibility survey in the exam room. iPad will be left in exam room for the study coordinator to collect directly after the visit. In the event that the electronic survey does not work (ex. technical issues), a paper copy of the survey will be provided to the subject to complete. If for any reason the subject is not able to complete the survey on site during the clinic visit, the study coordinator (or designated team member) may call the subject to complete the survey by phone.

Specimen pathway and processing (partnering with BAP/RLIMS): After visit is complete, the study coordinator or clinical staff will place the labeled subject-collected and clinician-collected specimens into a bag with the study card and leave it in the bin where Central Clinic Lab (CCL) specimens are placed for routine/non-study Gynecology appointments. The paired specimens will be sent from the Gyn Clinic (via General Service delivery) to the BAP group. BAP will accession the specimens, enter them into Soft and into the RLIMS system for tracking. The specimens will then be submitted to the Mayo Virology lab for HPV molecular testing by a commercially available (FDA-approved for clinician collected) testing platform (Roche Cobas HPV). The results will be collected by BAP and periodic reports will be issued for the study team.

Test result management: Through the written informed consent process, subjects will be informed that the primary HPV tests performed as part of this study (by patient vaginal self-sampling and provider cervical sampling) are not a replacement for recommended routine cervical cancer screening or for surveillance (recommended followup of abnormal Pap, HPV, colposcopy biopsy or precancer treatment). Because vaginal HPV testing of a self-collected sample is not FDA-approved, those results will not be reported to the accrued subject or to the Gynecology healthcare provider performing the clinician-collection of a cervical sample. The informed consent will note that subjects should continue with any screening procedures or testing as recommended by their healthcare provider.

The HPV test results of the clinician-collected research cervical sample will not be reported to the accrued subjects or to the clinician who collected the sample. This is because previously obtained HPV test results from clinical encounters should guide management, not research study results. As well, there is no reason to repeat an HPV test sooner than clinically indicated, whether that is for screening or surveillance after abnormal cervical

cytology, HPV, colposcopy biopsy or LEEP procedure. If patient is due for a clinical specimen collection the day of the visit in which self-sampling and clinician research-sampling will be done, that will be collected and that result will be part of the medical record and will guide management.

For a situation in which only a self-collected sample is obtained in absence of a clinician-collected research sample, the self-sample will be sent to the BAP lab and then onto the Virology lab as per the usual method.

In the event that the clinician-collected research cervical swab is not completed or is otherwise not useable (examples include but are not limited to: damaged in transport, has insufficient cellular material for testing, is not located due to loss in transport), the study team may access the patient's Epic medical record to look for a clinician-collected cervical swab done for clinical purposes (for HPV testing) within one week before or after the date of the patient self-collected vaginal specimen. In these instances, the participant will not be called back in to provide another sample.

Identification of subject demographics: The study will identify sociodemographics of accrued subjects through review of electronic medical record (age, race/ethnicity, insurance status, education, BMI, gravidity and parity, menstrual status, geography of residence/Rural-Urban Commuting Area codes/RUCA, SDOH profile from Epic including tobacco history, transportation needs, financial resource strain of the subjects) for use in the data analysis of the HPV test results and subject survey results.

Subject remuneration: Accrued study subjects who complete the vaginal self-sampling with the Evalyn brush, the clinician-collected cervical sampling and the electronic survey will receive \$50 in remuneration. Payment will be prorated for those unable to complete the whole study as outlined in the consent form.

Process flow for phase 2 includes the same identification and enrollment procedures, however the study team will need to ensure remote enrollment is complete before mailing an Evalyn brush self-sampling kit (including instructions for collection, labels for specimen container and bag, BAP lab form and pre-metered return mailing envelope) to their home. The kit will be mailed out prior to their clinic appointment and study subjects will be instructed to collect the sample at home and mail it back prior to the clinic appointment. On the day of the clinic appointment, a study team member will provide the subject with the electronic survey via iPad to be completed at the visit (if self-collected sample was done at home prior to the visit).

Specimen pathway and processing (partnering with BAP/RLIMS): The study subject-collected vaginal specimen will be mailed back via USPS to BAP and from that point forward, the specimen pathway and processing is unchanged in phase 2. For the clinician-collected cervical specimen, the specimen pathway and processing is unchanged in phase 2.

In the event that the subject has not enrolled remotely, they may still enroll and participate in the study if willing and able to enroll on site at the appointment, have a self-collection kit mailed to their home, collect the Evalyn brush sample at home on days 7-21 post-clinic appointment, mail the specimen back in as directed, and complete the survey by email or phone.

If the study subject has enrolled but does not collect the vaginal self-swab at home before the clinic appointment and wishes to complete the study, they may complete the Evalyn brush self-collection at home on days 7-21 post-Gynecology or Colposcopy appointment, mail it back and complete the survey by email or phone.

Added Lab evaluation for specimen stability:

Time-based stability testing: One HPV-positive study subject will be enrolled to collect 3 Evalyn Brush vaginal samples at their clinic visit. Those samples will be processed by the Mayo Virology lab following the same process outlined earlier in the Methods section for phase 1 and phase 2. However, processing will be performed at approximately 24 hours, 48 hours and 5 days after collection to determine how long after collection the Evalyn brush samples are stable prior to processing.

Temperature extremes stability testing: Four study subjects will be enrolled, two HPV-positive study subjects and two HPV-negative study subjects. Each study subject will collect 2 Evalyn Brush vaginal samples at their clinic visit. One sample from each of the study subjects' collections will be tested for HPV without temperature extreme stability testing. In order to assess for potential extreme temperature impact on sample and analyte stability during transportation from the home to the laboratory for mailed test kits, the second sample will be evaluated by the Food and Drug Administration (FDA) winter or summer temperature cycling profiles (1 HPV-positive swab for summer profile, 1 HPV-positive swab for winter profile, 1 HPV-negative swab for summer profile, 1 HPV-negative swab for winter profile) Samples will be tested following completion of the temperature cycling and qualitative results compared to results acquired following initial testing.

The process for identifying potential study subjects for the specimen stability aim component of the study will be identical to the process outlined in Methods for phase 1 and phase 2, other than there will be review of past cervical HPV test results to ensure 3 HPV-positive and 2 HPV-negative study subjects are included. The pre-appointment consent process will be identical to that outlined in Methods for phase 1 and phase 2, other than a new consent form will be created to reflect the specimen stability evaluation details outlined here.

Study subjects enrolled for the specimen stability aim will NOT have a clinician-collected cervical research sample nor will they be given the survey.

Remuneration: Accrued subjects who complete the required number of self-sampling collections (2 - 3), will receive \$50 in remuneration.

Subject Information

Target accrual is the proposed total number of subjects to be included in this study at Mayo Clinic. A "Subject" may include medical records, images, or specimens generated at Mayo Clinic and/or received from external sources.

Target accrual: Up to 250

Subject population (children, adults, groups): Adults aged 25-65 years old.

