2. Descriptive, bivariate, and multivariate analyses of acceptability/feasibility of patient self-sampling for cervical cancer screening and associations with patient sociodemographic characteristics.
3. For stability testing component of study, we will analyze concordance of multiple self-collected Evalyn brush HPV results within the same study subject.

Endpoints

1. Primary: Sensitivity and specificity of patient-collected vaginal swab to detect HPV infection compared with gold standard of clinician-collected cervical swab.
2. Secondary: Patient perspectives on acceptability and feasibility of HPV self-sampling for cervical cancer screening by sociodemographic characteristics.
3. Tertiary: Time-based and temperature extreme stability testing results.

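### The stability tests compare HPV calls without recording how much virus the positive brushes carry, so agreement cannot separate no loss from large loss in a strong positive

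*Combined protocol and SAP*

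**What the plan says.** The Phase 3 aim is to make sure that a delay before processing and "exposure to hot and cold temperatures will not impact the HPV test results".

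Under Added Lab evaluation for specimen stability, the temperature arm is introduced with a wider purpose: "In order to assess for potential extreme temperature impact on sample and analyte stability during transportation". It has four subjects, two HPV-positive and two HPV-negative. "Each study subject will collect 2 Evalyn Brush vaginal samples at their clinic visit"; one is tested without cycling and the other goes through a summer or winter profile. The positive samples are split as "1 HPV-positive swab for summer profile, 1 HPV-positive swab for winter profile". The comparison is then: "Samples will be tested following completion of the temperature cycling and qualitative results compared to results acquired following initial testing".

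The time-based arm has one HPV-positive subject who collects three brushes, processed at about 24 hours, 48 hours and 5 days.

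For both arms, Data Analysis Plan item 3 says "we will analyze concordance of multiple self-collected Evalyn brush HPV results within the same study subject". The endpoint list names no metric: "Tertiary: Time-based and temperature extreme stability testing results". HPV-positive and HPV-negative subjects are identified from past cervical HPV results. The Background describes the test as "using a polymerase chain reaction-assay (PCR) that is FDA-approved for clinician-collected HPV testing". The document does not mention cycle-threshold (Ct) values, a signal cut-off, a weakly positive sample or a limit for acceptable change.

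**The concern.** A positive call says that the signal crossed a threshold, not by how far. If a brush starts well inside the threshold, much of its target can be lost before the call changes. The loss that matters for mailed kits is the loss that turns a weak positive negative, and agreement of calls in a strong positive does not inform that.

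The plan neither requires nor records a load, so a reader of the results could not tell which kind of sample was tested. Full concordance might then be cited as general support for mailing, when it covers only a handful of brushes of unknown starting value.

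The compared brushes are also collected separately, and no rule links collection order to test condition. A difference in yield between brushes could therefore look like degradation, or hide it.

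**Working it through.** The plan states no figure for this aim, so there is none to reproduce. The check has four steps.

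**1. What carries information on loss.** Positive subjects: 1 (time) + 2 (temperature) = 3. Negative subjects: 2. Brushes: 1 × 3 + 4 × 2 = 11. A negative brush has no detectable target to lose, so two of the four temperature pairs bear on degradation, one per profile. The time arm rests on one subject.

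**2. How much loss a positive call can hide.** The document gives no Ct, cut-off or amplification efficiency, so these inputs are assumptions. Let *h* be the cycles of headroom inside the cut-off and *E* the amplification per cycle. The share of target that can be lost with the call still positive is 1 − E^(−h).

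| Headroom *h* (cycles) | E = 2.0 | E = 1.8 |
|---|---|---|
| 1 | 50.0% | 44.4% |
| 5 | 96.9% | 94.7% |
| 10 | 99.9% | 99.7% |

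For example, 1 − 2^(−5) = 1 − 1/32 = 96.9%. A brush with 1 cycle of headroom turns negative after roughly half its target is lost; one with 10 cycles stays positive until almost all is gone. The same concordant result means very different things in the two cases.

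**3. What a Ct value would show.** A loss *L* shifts Ct by log(1/(1 − L)) / log(E), provided the brush is still positive.

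| Loss | Shift, E = 2.0 | Shift, E = 1.8 |
|---|---|---|
| 90% | 3.3 | 3.9 |
| 99% | 6.6 | 7.8 |
| 99.9% | 10.0 | 11.8 |

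**4. How much of that shift is readable from one pair.** The two brushes are separate collections. With an assumed brush-to-brush SD, the 95% band for one difference is ±1.96 × √2 × SD.

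| Assumed SD (cycles) | Band (cycles) | Losses above that stand out |
|---|---|---|
| 0.5 | ±1.4 | 90%, 99%, 99.9% |
| 1 | ±2.8 | 90%, 99%, 99.9% |
| 2 | ±5.5 | 99%, 99.9% |
| 3 | ±8.3 | 99.9% |

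Across this range, Ct reliably reveals gross loss. It does not measure moderate loss, because there is one pair per condition and no replicate.

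**The case against.** The strongest reply is that a qualitative comparison matches the Phase 3 aim, which speaks of the HPV test result, and that the primary endpoint is also a detected/not-detected outcome. This stands for the samples tested. It does not meet the analyte purpose stated for the temperature arm, nor does it extend to weak positives.

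Second, a reader might infer that losses in home use would go unnoticed. The document does not support that. Phase 2 compares mailed, home-collected brushes with clinician samples in at least 74 patients, with sensitivity as a primary endpoint, so positives lost in ordinary mailing would appear as false negatives. Phase 2 does not control delay or temperature and mixes degradation with sampling differences, so it does not replace the stability test.

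Third, the word qualitative is explicit only for the temperature arm. For the time arm, the reading rests on the word concordance in the analysis plan. This limit stands.

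Fourth, nothing says the enrolled positives will be strong. A weak positive would make the call a sensitive measure. This is true, and the difficulty is that the planned data would not show which case applied.

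Fifth, a reader might infer that alternating which brush is left untreated would remove the order effect. It would not. With one positive subject per profile, order stays confounded with profile, the negative subjects supply no HPV signal from which to estimate it, and the time arm has a single subject. Recording the order is useful; it does not solve the problem.

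**Conclusion.** The point holds in a limited form. The temperature arm has a purpose that includes the analyte and a measure that registers only a change of call; the time arm appears to use the same measure. Since load is neither required nor recorded, a concordant positive pair cannot separate no loss from large loss, and it supports no statement about weak positives.

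The size is illustrative. At two-fold amplification, the loss that could be hidden is about 97% with 5 cycles of headroom and 99.9% with 10; at 1.8-fold, about 95% and 99.7%. These figures rest on assumed efficiency and headroom, and the brush-to-brush SDs are likewise assumed. That a Ct value lies behind each positive call, and that it can be exported, is also an assumption, since the document says only that the assay is PCR.

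This is a tertiary endpoint in five subjects with no inference planned, so the point is a modest one. It is worth acting on because the remedy draws more from tests already planned. It does not affect the primary comparison.

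**What to change.** In the time-based and temperature paragraphs of Added Lab evaluation for specimen stability, and in Data Analysis Plan item 3:

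- Keep the qualitative comparison, and say explicitly whether concordance in the time arm means agreement of calls.
- Record the Ct value of every brush, once the laboratory confirms that the platform exports it.
- Record the collection order of each brush on its label.
- Report the within-subject Ct shift descriptively, from the untreated brush in the temperature arm and from the 24-hour brush in the time arm. State that one comparison of separately collected brushes per condition can distinguish only gross loss from brush-to-brush variation.
- State stability only for the range of starting values tested.

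This needs no added subjects, samples or tests: an export of run data and a number on the label. If Ct values cannot be exported, recording order remains possible, and the conclusion should then be limited to the samples tested, with a note that their starting load is unknown. The downside is a narrower stability statement.
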